## 15.2 Analysis of Efficacy

For all analyses, baseline will be considered as information collected on Day 0 prior to device start. For investigational drug-device use, the device start date and time will be used as the reference datapoint.

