6.2.2. Treatment Phase (Day 0)

After the screening activities have been completed and laboratory analyses reviewed to confirm eligibility, the patient may be randomized (2:1) to receive either Furoscix or continued medical therapy with oral diuretics. Subjects randomized to continued medical therapy will follow the same schedule of assessments, excluding study product administration.

The initial dose of the study product should be administered after randomization. If randomized to Furoscix, product training with subject and/or caregiver will be conducted. The initial dose of the study product may be administered in the clinic or at home on the day of enrollment. Study staff will dispense additional doses of Furoscix. Subjects will be provided a Subject Diary in which to record any observed device issues and self-assessments that will be completed at home.

The Subject will be reminded to use the provided equipment to weigh themselves and record their blood pressure and heart rate and complete the patient global assessment VAS upon returning home and first thing in the morning on Day 1. They will also be reminded to bring their study product (device) and Subject Diary back to the clinic on Day 1.

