6.2.17. Vital Signs

Vital signs will be conducted during screening (Day 0). Vital signs will include respiratory rate (respirations per minute), blood pressure (mmHg) and heart rate (beats per minute [bpm]). Vital signs will be obtained after the Subject has been resting in sitting position for 5 minutes.

Height and weight will be collected for BMI. Height collected Day 0 only.

On Days 1-30 weight, heart rate and blood pressure will be obtained by the Subject at home using the equipment supplied at screening and recorded daily in the Subject Diary. These will be collected at home in the morning even for those days where visits to the clinic are required.

Vital signs (respiratory rate, blood pressure, heart rate) will also be collected at each in-clinic visit. Weight will also be collected at each in-clinic visit.

6.2.18. % Lung Fluid Measurement (ReDS)

The ReDS System is a non-invasive diagnostic device consisting of a Bedside Console connected to a wearable Sensor Unit that is used for the measurement of lung fluid. The system is FDA cleared for use by qualified healthcare practitioners, under the direction of a physician, in hospitals, hospital-type facilities and home environments, for the non-invasive monitoring and management of patients with fluid management problems in a variety of medically accepted clinical applications.

The ReDS System is indicated for patients:

- With fluid management problems
- Taking diuretic medications
- Living with heart failure
- Recovering from a coronary artery disease-related event

The Sensor Unit consists of two sensors and a positioner. One sensor is placed on the patient's upper right chest through light clothing and another on the upper-right part of the patient's back. The Sensor Unit is connected by a non-detachable cable to the Bedside Console. Low power electromagnetic (EM) signals are emitted and pass through the thorax and software in the console calculates an average dielectric coefficient that reflects the percentage of lung tissue fluid content.

The system provides an on-screen reading within 45 seconds. Measurements are recorded in units of percent (%), representing the percent of lung tissue volume that is occupied by fluid. The normal value of lung fluid volume ranges between 20% and 35%. The full range of lung fluid volume provided by the ReDS system spans from 15% to 60%.

Study Staff will be trained on the use of the ReDS system.

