## 9. DEFINITIONS

**Baseline:** Baseline is defined as the last non-missing value prior to the first administration of the study drug, unless otherwise stated.

**Change from Baseline:** The change from baseline values will be calculated as post-baseline value (p) minus the baseline value (b).

**Percent (%) Change from Baseline:** The % change from baseline values will be calculated as  $(p - b)/b \times 100$ .

**Adverse Event (AE):** Any untoward medical occurrence associated with the use of an Investigational Product (IP) in humans, whether considered related to the IP and does not imply any judgment about causality. The Investigator will assess each AE for seriousness as defined in the protocol and severity and causality based on their best medical judgment, the observed symptoms associated with the event, and the available information on the Investigational Product (IP) as defined in the protocol. The relatedness guidance provided below can be used to assist in determining the relationship of the IP to the AE.

- **Not Related:** Based upon available information regarding subject history, disease process, relationship of adverse event to dosing and drug pharmacology, there is no reasonable relationship between the IP and the adverse event.
- **Possibly Related:** Relationship exists between the adverse event and IP, when the adverse event follows a reasonable sequence from the time of the IP administration, but could also have been produced by the subject's clinical state or by other drugs administered to the patient.
- **Probably Related:** Relationship exists between the adverse event and the IP when the adverse event follows a reasonable sequence from the time of IP administration, follows a known response pattern of the drug class, is confirmed by improvement on stopping the IP and the IP is the most likely of all causes.
- **Definitely Related:** Relationship exists between the adverse event and the IP when the adverse event follows a reasonable sequence from the time of the IP administration, follows a known response pattern of the drug class, is confirmed by improvement on stopping the IP and no other reasonable cause exists.

**Treatment-emergent Adverse Events (TEAEs):** A treatment-emergent adverse event (TEAE) is any new AE that emerges on or after the start of the first study drug administration having been

absent in pre-treatment (or) worsen in severity relative to the pre-treatment state following administration of study drug.

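### Efficacy baseline is tied to first dose or device start, not randomization, so a post-allocation home weight or VAS can become baseline for part of the Furoscix arm

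*SAP*

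**What the plan says.** The SAP has two baseline rules. SAP 9 (Definitions) says: "Baseline is defined as the last non-missing value prior to the first administration of the study drug, unless otherwise stated". SAP 15.2, for efficacy, says: "For all analyses, baseline will be considered as information collected on Day 0 prior to device start", and adds: "For investigational drug-device use, the device start date and time will be used as the reference datapoint". SAP 15 gives the SAP precedence over the protocol, and the protocol's statistics section has no baseline definition of its own.

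On Day 0, clinic weight and VAS are collected at screening (Protocol 6.2.1), and randomization follows once screening is complete (Protocol 6.2.2). The same section then says: "The initial dose of the study product should be administered after randomization", and: "The initial dose of the study product may be administered in the clinic or at home on the day of enrollment". It also has subjects reminded to "weigh themselves and record their blood pressure and heart rate and complete the patient global assessment VAS upon returning home", and again the next morning. Controls follow the same assessments without study product. The study is open label (Protocol 5.6).

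SAP 15.2.2 models change from baseline in VAS and in body weight by GEE, with the baseline value also a covariate.

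**The concern.** Both SAP rules use an event that exists only in the Furoscix arm and comes after allocation is known. Between randomization and a first dose at home, the protocol asks for a second weight and a second VAS. A rule that takes the last value before dosing can pick up that second reading in home-dosed Furoscix subjects and in no one else.

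The source of the baseline could then differ by arm and, within the Furoscix arm, by place of first dose. For weight, any systematic gap between the home and clinic readings would appear as a treatment difference. For VAS, a patient's reaction to learning the allocation could enter the baseline and be subtracted from the effect. A covariate measured after allocation also loses the protection of randomization. Weight and VAS are two of the ten secondary endpoints in a pilot whose stated purpose includes refining pivotal endpoints.

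**Working it through.** There is no planned figure to reproduce. SAP 4 reports no power analysis, and the documents give no SD, home-dosing share or home-clinic offset. The allocation is 51 × 2/3 = 34 Furoscix and 51/3 = 17 control.

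**Step 1. Which Day 0 value does the text select?**

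| Subject | Day 0 values available | Value selected on a literal reading |
|---|---|---|
| Furoscix, dosed in clinic | clinic before dose, home after dose | clinic |
| Furoscix, dosed at home, readings before device start | clinic, then home, both before dose | home (SAP 9); not specified (SAP 15.2) |
| Furoscix, dosed at home, readings after device start | clinic before dose, home after dose | clinic |
| Control | clinic and home, no dose | no rule |

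SAP 15.2 admits both values in the second row without choosing. SAP 9 chooses the later one.

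**Step 2. Which endpoints are exposed?** NT-proBNP, CCS, 5-point dyspnea, KCCQ-12, creatinine, 6MWT and ReDS have Day 0 values from clinic screening only. The 7-point dyspnea score and days alive and event-free use no baseline. That leaves weight and VAS.

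**Step 3. Which days?** Let δ be the home-minus-clinic offset and W the clinic weight, with no true change. Compare a Furoscix subject with a home baseline and a control with a clinic baseline.
- Home-weight day: Furoscix (W+δ) − (W+δ) = 0; control (W+δ) − W = δ; difference −δ.
- Clinic-weight day: Furoscix W − (W+δ) = −δ; control W − W = 0; difference −δ.

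The difference is the same on both kinds of day. Only the baseline mismatch matters.

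**Step 4. Size.** Let h and c be the shares of Furoscix and control subjects with a home baseline, and ρ the slope of follow-up on baseline. In a baseline-adjusted change analysis, bias = −ρ(h − c)δ. This was checked by simulation: 4,000 runs per case, 34 vs 17, no true effect, one follow-up time, and least squares in place of GEE. All inputs except the arm sizes and the two-sided 0.05 level are assumptions: ρ = 0.99 and SD 20 kg for weight, ρ = 0.5 and SD 20 points for VAS.

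| Endpoint | δ | h | c | Formula | Simulated mean | Type I error |
|---|---|---|---|---|---|---|
| Weight, kg | 0.5 | 0.25 | 0 | −0.12 | −0.13 | 0.049 |
| Weight, kg | 0.5 | 0.5 | 0 | −0.25 | −0.25 | 0.057 |
| Weight, kg | 1.5 | 0.5 | 0 | −0.74 | −0.73 | 0.133 |
| Weight, kg | 1.5 | 1 | 0 | −1.49 | −1.46 | 0.396 |
| Weight, kg | −1.5 | 0.5 | 0 | +0.74 | +0.75 | 0.138 |
| Weight, kg | 1.5 | 0.5 | 1 | +0.74 | +0.76 | 0.131 |
| Weight, kg | 1.5 | 0.5 | 0.5 | 0 | −0.02 | 0.049 |
| VAS, points | 3 | 0.25 | 0 | −0.38 | −0.47 | 0.054 |
| VAS, points | 10 | 0.5 | 0 | −2.50 | −2.34 | 0.073 |
| VAS, points | 10 | 1 | 0 | −5.00 | −4.92 | 0.144 |

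Example: −0.99 × (0.5 − 0) × 1.5 = −0.74 kg. The sign reverses with the sign of the offset, or if controls take the home value. Equal shares give zero, provided the offset is the same in both arms; for VAS in an open-label trial it need not be.

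**Step 5. After the fix.** With h = c = 0 the formula gives 0, and simulated type I error was 0.047 to 0.055.

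**The case against.** The strongest reply is that the Day 0 home reading may not be analysis data at all. Protocol 6.2.17 says: "On Days 1-30 weight, heart rate and blood pressure will be obtained by the Subject at home using the equipment supplied at screening", which leaves out Day 0. Footnote 2 of the Time and Events Schedule (Protocol Appendix 1, SAP Table 1) likewise starts home readings after Day 0, and the Day 0 column in Appendix 1 is a clinic column. Protocol 6.2.19 lists the VAS for Day 0 without a second reading. SAP 7.1 treats repeat assessments as unscheduled and keeps unscheduled visit data out of tables. Also, SAP 9 yields wherever something else is stated, SAP 15.2 does not ask for the last value, and nothing requires the home reading to come before device start.

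Much of this stands: it is not established that any home reading would become a baseline. It does not remove the problem. Protocol 6.2.2 asks for the reading explicitly, the two texts that start home readings after Day 0 cover weight and vital signs but not VAS, and SAP 7.1 neither classes this reading as a repeat nor bars it from the baseline derivation.

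A reader might infer that controls have no baseline. They do have a Day 0 clinic value; what they lack is a rule for choosing it over the home one. A reader might also infer that the false difference is confined to days with home weights only, and that home weights should therefore leave the model. Step 3 shows otherwise.

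**Conclusion.** The concern holds as a conditional one. The written rules allow an arm-dependent baseline for weight and VAS, and the documents do not settle whether it would occur. Bias requires all of the following: home readings taken before device start, their entry into the baseline derivation, a non-zero home-clinic offset, and unequal shares between arms (or, for VAS, offsets that differ by arm).

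If these are met, the error is about (h − c)δ for weight, where the slope is near 1, and a smaller multiple for VAS. Over the assumed ranges with controls on the clinic value (h from 0.25 to 1), it runs from 0.12 to 1.49 kg for weight offsets of 0.5 to 1.5 kg, and from 0.4 to 5.0 points for VAS offsets of 3 to 10 points. At the low end, type I error is essentially nominal. These figures illustrate scale; they do not estimate what happens in this trial.

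The documents do not support the stronger readings that the comparison is biased as a matter of fact, that the direction is known, or that the primary composite is compromised. NT-proBNP, its only baseline-dependent component, has no post-allocation Day 0 sample.

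**What to change.** In SAP 9 and 15.2, define efficacy baseline in both arms as the last value obtained before randomization; for weight and VAS this is the Day 0 clinic screening value. State that Day 0 readings taken after returning home are post-randomization and never baseline.

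Home weights can stay in the weight model. With a common clinic baseline, a home-clinic offset at follow-up cancels between arms, provided the same source is used in both arms on a given day and the offset does not depend on arm. Removing them would lose Days 2, 4, 5, 6 and 17, five of the nine scheduled follow-up contacts, and would depart from the ambulatory body weight endpoint in Protocol 8.4.2.

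The cost is a sentence or two in two SAP sections and a flag on the Day 0 home readings in the analysis dataset. No new data are needed, and study procedures do not change.

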### 15.2.1 Primary Efficacy Analysis

The primary efficacy endpoint is the improvement in a composite/combined morbidity/mortality endpoint at 30 days using the Finkelstein Schoenfeld method. The analysis of the primary efficacy endpoint will be conducted for the ITT and PP populations. Each component of the primary endpoint will be compared in pairwise fashion hierarchically. Each patient is compared to all other patients with respect to each of the following endpoints hierarchically. The algorithm is as follows when doing a pairwise comparison of Patient B to Patient A:

- CV death at 30 days:
  - if Patient A survives to 30 days and patient B dies before 30 days, then score = -1 for Patient B
  - if Patient B survives to 30 days and patient A dies before 30 days, then score = +1 for Patient B
  - if both patients survive or if both die , then move to the comparison on the next component.
- HF hospitalization at 30 days:
  - if Patient A is not hospitalized for worsening heart failure (WHF) and patient B is, then score = -1 for Patient B
  - if Patient A is hospitalized for WHF and patient B is not, then score = +1 for Patient B
  - if both patients are not hospitalized or if both are hospitalized, then move to the comparison on the next component.
- Urgent ED/Clinic visit at 30 days for WHF (defined as IV diuretics, augmentation of or new administration of metolazone)
  - if Patient A does not have an Urgent/ED visit for WHF and patient B does have a visit, then score = -1 for Patient B
  - if Patient A does have an Urgent/ED visit for WHF and patient B does not have a visit, then score = +1 for Patient B
  - if both patients have an Urgent/ED visit for WHF, then move to the comparison on the next component.

- if both patients do not have an Urgent/ED visit for WHF, then move to the comparison on the next component.
- Percent Change in NT-proBNP from baseline at 7 days (without imputation):
  - if Patient A's change from baseline at 7 days in NT-proBNP < Patient B's change from baseline at 7 days in NT-proBNP, then score = -1 for Patient B
  - if Patient A's change from baseline at 7 days in NT-proBNP > Patient B's change from baseline at 7 days in NT-proBNP, then score = +1 for Patient B
  - If tied, score=0 for Patient B.

A -1/0/1 score is created for Patient B vs. every other patient in the study, so if there are  $n$  total patients in the study, then patient B is assigned  $n$  -1/0/1 scores (including, for completeness, a score of 0 when patient B is compared to themselves). Similarly, every other patient in the study is also assigned  $n$  -1/0/1 scores.

For each patient  $i$ , the sum of all -1/0/1 scores assigned to that patient is calculated and is denoted as  $U_i$ . If  $n1$  and  $n2$  are the number of patients in the experimental and control arms, respectively, then the lowest possible value of  $U_i$  that a given patient can experience is  $-(n1 + n2 - 1)$ , which is achieved if the given patient scored a -1 versus all other  $(n1 + n2 - 1)$  patients in the study; similarly, the largest possible of  $U_i$  that a given patient can experience is  $+(n1 + n2 - 1)$ .

The numerator of the estimate of  $T$  (the Finkelstein-Schoenfeld test statistic) is the sum of the  $U_i$  across patients assigned to the experimental treatment. i.e.,

$$\sum_{i=1}^n D_i U_i$$

where  $U_i$  is the sum of the -1/0/1 scores for the  $i^{\text{th}}$  patient in the sample,  $D_i$  is the indicator of the treatment group to which the  $i^{\text{th}}$  patient was randomized ( $D_i = 0$  for control and  $D_i = 1$  for experimental) and  $n$  is the total sample size.

The denominator of  $T$  is:

$$\sqrt{\frac{n1 * n2}{n * (n - 1)} \sum_{i=1}^n U_i^2}$$

where (a)  $n1$  and  $n2$  are the number of patients in the experimental and control arms, respectively; (b)  $n$  is the total sample size ( $= n1 + n2$ ); and (c)  $U_i$  is the sum of the -1/0/1 scores for the  $i^{\text{th}}$  patient in the sample. The test statistic follows a standard normal distribution; the two-sided p-value is the area in the upper and lower tails of  $T$  on the standard normal curve.

The primary efficacy endpoint will be repeated for the ITT and PP analysis populations using the Day 3 NT-proBNP value (instead of the Day 7 NT-proBNP value). The Day 3 NT-proBNP value will be used for calculating the percent change from baseline as follows:

- Percent Change in NT-proBNP from baseline at 3 days:
  - if Patient A's change from baseline at 3 days in NT-proBNP < Patient B's change from baseline at 3 days in NT-proBNP, then score = -1 for Patient B
  - if Patient A's change from baseline at 3 days in NT-proBNP > Patient B's change from baseline at 3 days in NT-proBNP, then score = +1 for Patient B
  - If tied, score=0 for Patient B.

A listing of each endpoint for the composite will be presented for the ITT population.

A sensitivity analysis will be conducted where the primary efficacy endpoint analysis will be conducted on the ITT and PP analysis population and will exclude patients with normal NT pro-BNP values (defined as <125 pg/mL) at baseline. Results will be descriptively compared to the primary efficacy endpoint analysis on the ITT and PP population.

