## 14. ANALYSIS POPULATIONS

**Intent-to-Treat (ITT):** ITT population will include all randomized subjects. The subjects in ITT population will be analyzed according to the treatment group they were originally randomized.

**Safety:** Safety population will include all randomized subjects who received at least one dose of Investigational Product (IP). The subjects in the Safety population will be analyzed and presented according to the actual treatment received.

**Per-Protocol (PP):** All randomized subjects who received at least one dose of the IP, completed the 30 Day clinic visit assessments and have a Day 7 NT-proBNP value available for analysis.

All effectiveness analyses, including the primary endpoint and baseline characteristics will be performed on the ITT and Per-Protocol populations. Safety analyses will be performed on the safety population.

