## 15. STATISTICAL ANALYSIS

This is a multicenter, randomized, open label, controlled study evaluating the effectiveness and safety of the Furoscix Infusor versus continued medical therapy in patients with chronic heart failure and fluid overload requiring augmentation in diuretic therapy outside of the acute care setting. The SAP takes precedence over the protocol.

Unless otherwise specified, all baseline data, including demographic data and other clinical characteristics will be compared using descriptive statistics grouped by treatment group (Furoscix On-Body Infusor vs Continued Medical Therapy for Worsening Heart Failure). Change from baseline is the absolute change, unless stated otherwise; which then will be percentage change from baseline. Tables will include footnotes indicating definition implemented. Continuous data will be summarized by reporting the number of observations, mean, standard deviation, minimum, median, and maximum values. Categorical data will be described using frequency tables showing the number and percentage of subjects falling within a particular category. Shift tables will be given where appropriate to show change at follow-up compared to baseline values.

Between-group analyses of baseline characteristics will employ descriptive statistics. Mortality and morbidity events will be assessed using appropriate statistical tests. The primary endpoint will be compared between treatments using the Finkelstein-Schoenfeld Method, comparing components of the composite endpoint between patients hierarchically. Given the nature of the study, there will be no imputation of missing data on endpoints.

The primary endpoints including CV death at 30 days, HF hospitalization at 30 days, Urgent ED/Clinic visit at 30 days for WHF (defined as IV diuretics, augmentation of or new administration of metolazone), and change in NT-proBNP from baseline at 7 days will also be summarized and analyzed separately.

In general, secondary efficacy with follow-up timepoints will be analyzed using Generalized Estimating Equations (GEE) models.

Statistical tests will be performed at a two-sided alpha level of 0.05, unless otherwise specified. Given the nature of the study, there will be no adjustment for multiple comparisons.

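### SAP 15.2.1 must score every ITT pair in the primary composite, but gives no rule for subjects whose follow-up is incomplete or whose NT-proBNP change is missing

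*SAP*

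**What the plan says.** The primary Finkelstein-Schoenfeld analysis is run on ITT and PP. SAP 14 states that "ITT population will include all randomized subjects", and SAP 15.2.1 that a -1/0/1 "score is created for Patient B vs. every other patient in the study". A subject who leaves early therefore needs a score in every ITT pair.

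The tiers in SAP 15.2.1 read as follows.

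- **Tier 1 (headed CV death):** "if Patient A survives to 30 days and patient B dies before 30 days, then score = -1 for Patient B", with the mirror rule. A pair moves on only if both survive or both die.
- **Tier 2 (HF hospitalization):** "if Patient A is not hospitalized for worsening heart failure (WHF) and patient B is, then score = -1 for Patient B", with the mirror rule. Tier 3 (urgent ED/clinic visit) has the same form. Neither requires observation to Day 30.
- **Tier 4:** "Percent Change in NT-proBNP from baseline at 7 days (without imputation", with scores for lower, higher and tied only.

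SAP 15 adds: "Given the nature of the study, there will be no imputation of missing data on endpoints". The composite is repeated with "Percent Change in NT-proBNP from baseline at 3 days" on ITT and PP. PP requires that subjects "completed the 30 Day clinic visit assessments and have a Day 7 NT-proBNP value available for analysis"; it does not require a Day 3 value. The one sensitivity analysis of the composite excludes subjects with baseline NT-proBNP below 125 pg/mL and does not address dropout.

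**The concern.** An early dropout falls through the algorithm at three points. At tier 1 the subject is neither a Day 30 survivor nor a death. At tiers 2-3 the literal wording makes a subject lost on Day 5 with no event not hospitalized, so that subject beats one followed throughout and admitted on Day 20. At tier 4 a missing value is not lower, higher or tied. Ruling out imputation does not settle this: scoring 0, ranking the subject last and excluding the subject all avoid filling in a value, yet give different statistics.

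Tier 1 has a further ambiguity. Its heading is CV death but its rule says only that the subject dies, so a non-CV death has no clear place.

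The trial is open label, so unequal loss between arms is plausible. The ITT result would then depend partly on a coding choice made after outcomes are visible. One secondary objective is to refine endpoints and analytical methods for the pivotal trial (SAP 6.2), so an unstated rule could be carried forward.

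**Working it through.** **Inputs.** From the documents: 34 vs 17 subjects (SAP 4), two-sided alpha 0.05 (SAP 15) and the formula for T (SAP 15.2.1). The documents give no event or dropout rates and no power calculation, so every rate below is an assumption. Positive T favours Furoscix.

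**1. Scale of T.** With no ties, the U values are 50, 48, ..., -50 and their squares sum to 44,200. The denominator is sqrt[34 × 17 / (51 × 50) × 44,200] = 100.09, so 100 net points in the numerator is about one unit of T.

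**2. What the choice of rule does in one data set.** Within-arm pairs cancel in the numerator. Coding dropouts as event-free, rather than as unknown with score 0, changes it by d_F·e_C - d_C·e_F, where d is dropouts without an event, e is subjects with an event, and F and C are the arms. Take events in 7/34 and 5/17; with complete data T = 78/100.1 = 0.78.

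- Four Furoscix dropouts: 4 × 5 - 0 × 7 = +20.
- Three control dropouts: 0 × 5 - 3 × 7 = -21.

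| Rule for dropouts | 4 Furoscix lost | 3 control lost |
|---|---|---|
| Event-free at tiers 2-3, missing NT-proBNP = 0 | 70/93.7 = 0.75 | 35/95.2 = 0.37 |
| Unknown at tiers 2-3 scores 0 | 50/88.5 = 0.57 | 56/91.4 = 0.61 |
| Dropouts excluded | 50/90.3 = 0.55 | 56/88.2 = 0.64 |
| Event-free, missing NT-proBNP ranked worst | 22/100.1 = 0.22 | 116/100.1 = 1.16 |

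The tier 4 rule moves T at least as much as the tier 2-3 rule does.

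**3. Null simulation, loss unrelated to risk.** Times to death, admission and urgent visit are exponential, with Day 30 rates of 2/15/10%, 3/20/10% or 5/25/15%. NT-proBNP change is normal and missing if follow-up ends before Day 7. Exits are uniform over Days 0-30 or Days 0-10. There were 3,000 to 12,000 runs per setting.

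| Loss, Furoscix vs control | Rule | Mean T | Two-sided error |
|---|---|---|---|
| 20% vs 5% | Event-free, missing = 0 | +0.10 to +0.30 | 4.4-6.5% |
| 5% vs 20% | Event-free, missing = 0 | -0.11 to -0.31 | 4.6-5.5% |
| 20% vs 5% | Event-free, missing ranked worst | -0.29 to +0.06 | not tabulated |
| 20% vs 5% | Unknown scores 0 | -0.06 to -0.15 | not tabulated |
| 20% vs 5% | Shared follow-up at all event tiers | within 0.02 of 0 | 4.2-5.6% |
| 20% vs 5% | All deaths counted, shared follow-up at tiers 2-3 | up to about 0.05 | 4.3-5.7% |
| 30% vs 0%, exits Days 0-10 | Event-free, missing = 0 | +0.41 to +0.59 | 7.9-9.0% (12,000 runs), about 8-11% (3,000 runs) |
| 10% vs 10% | Event-free, missing = 0 | about 0 | 4.5-5.3% |

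**4. Loss related to risk.** Let 30% of subjects carry three times the hazard and, on Furoscix, be three times as likely to leave (20% vs 5%). Event-free coding with missing = 0 gives mean T +0.14 to +0.38 and error 5.2-7.2%. Shared follow-up at all event tiers leaves +0.04 to +0.11 and 5.0-5.7%. In a harsher case, 4 of 34 Furoscix subjects and no controls are lost, mainly the sicker ones. Event-free coding then rejects in 7.4/8.9/10.0% of trials at event rates of 10/20/30%. Excluding dropouts still gives 7.2% at 20% and at 30%, so it does not remove the whole excess.

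**5. Day 3 repeat.** The Day 3 sample was added in Amendment 5, so none was scheduled for anyone enrolled earlier. A pair can be compared on Day 3 only if both values exist. If 10%, 25% or 50% lack one, that share is 0.90² = 81%, 0.75² = 56% or 0.50² = 25% of pairs. The documents do not say how many subjects preceded the amendment.

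**The case against.** **The event-free rule is not written.** This is correct. Read strictly, a dropout stalls at tier 1 and never reaches tiers 2-3. A reader might infer that the SAP deliberately counts dropouts as event-free, or that T always moves toward the arm losing more subjects. The documents support neither. Event-free coding is the literal effect of the tier 2-3 wording once tier 1 is passed, and the shift vanishes or reverses if a missing NT-proBNP is ranked worst. What stands is that some rule must be chosen and none is stated.

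**The plan limits and displays the problem.** Contact is daily to Day 7, survival and HF events are assessed through 30 ± 5 days (Protocol Synopsis), and withdrawn subjects should have the follow-up assessments as far as possible (Protocol 4.3). The SAP tabulates withdrawals with reasons and lists each composite endpoint. These steps make unknown status rarer and visible, but do not score it.

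**PP covers it.** PP largely protects the Day 7 analysis, but supplies no ITT score and does not protect the Day 3 repeat. Its requirement of a dose of investigational product raises a separate question for controls.

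**It is a small exploratory pilot without a power claim.** This limits the severity, and the effect at moderate imbalance is indeed small.

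**Scoring 0 whenever status is unknown would be simpler.** It closes the textual gap, but the simulation shows a bias in the opposite direction (-0.06 to -0.15 at 20% vs 5%), which shared follow-up largely avoids.

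**Conclusion.** The gap is real and lies in the primary analysis. SAP 15.2.1 demands a score for every ITT pair without a follow-up condition at tiers 2-3, a tier 1 status for unknown survival, or a tier 4 score for a missing value. The Day 3 repeat shares the tier 4 gap, also in PP.

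The consequence is conditional. With equal loss there is no bias. At 20% vs 5% the mean of T moves by roughly 0.1 to 0.3 in size, in a direction set by the unwritten tier 4 rule. With missing scored 0 and loss unrelated to risk, error stays near nominal except at extreme early imbalance; if sicker subjects leave one arm it can be higher. A reader might infer that the primary test is seriously invalid; at plausible moderate loss these figures do not support that. Yes/no scoring itself is a legitimate choice. The point is worth correcting because the remedy is cheap and should be fixed before outcomes are examined. All sizes rest on assumed event and dropout rates.

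**What to change.** Keep yes/no scoring and add to SAP 15.2.1:

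> Every observed death of the tier 1 type counts at tier 1; a subject with no recorded death is treated as not dead at that tier. At tiers 2-3 each pair is compared over its shared follow-up, the shorter of the two, capped at Day 30, and an event counts only if it falls inside that window. Follow-up ends at the last contact with known event status; a subject who completes the Day 30 ± 5 visit is treated as followed to Day 30. At tier 4, and in the Day 3 repeat, the score is 0 if either percent change is missing.

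State whether tier 1 is CV or all-cause death. Apply the same rules to the analysis excluding baseline values below 125 pg/mL. Report two sensitivity analyses: status-by-Day-30 scoring, and missing NT-proBNP ranked worst.

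**Cost.** A few sentences and one change to the scoring program, with no extra subjects or visits. There are three downsides.

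- Some observed admissions and urgent visits after a partner's last contact no longer count in that pair. If deaths were windowed too, 16 to 42 of the 34 × 17 = 578 between-arm pairs would be affected at 20% vs 5%, of which 1.4 to 5.5 involve deaths. The wording above keeps those deaths.
- Counting all deaths leaves a small residual bias: mean T up to about 0.05 at 20% vs 5% and 0.09 at 30% vs 0%.
- Event dates and a last-contact date are needed. Serious adverse event reports carry an onset date (Protocol 7.7.2), but Protocol 9.1.7 requires only the reason for withdrawal on the CRF. Confirm that last-contact and urgent-visit dates are captured.
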